9.7.3 Sensitivity analyses

Sensitivity analyses will be performed to assess the robustness of the study findings:

 The assumptions underlying the construction of NOCDURNA treatment episodes will be tested. The length of the permissible gap will be varied (shortened or lengthened). For overlaps of two subsequent prescriptions, beginning of the second prescription will be shifted to the end of the first. The estimation of prescription duration will also be examined. Instead of estimating prescription duration based on the recommended daily dose of NOCDURNA (1 oral lyophilisate), the dose actually prescribed to the individual patient will be considered (Sweden, Denmark). This analysis will be subject to availability of data on individual dosage instructions in the database/registry.

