9.3 VARIABLES

9.3.1 Exposure

Person-time observed from index date to the date of outcome or censoring event will be determined for both the NOCDURNA group and the LUTS group.

Person-time exposed will start accumulating from the index date. For the NOCDURNA group this will be the date that the first-ever prescription for NOCDURNA was dispensed. Thus, this study will include patients who are new users of NOCDURNA. For the LUTS group, this will be the date of a first-ever prescription of a drug with the ATC code G04BD or G04C within the study time period. Thus, the LUTS groups will include patients who are new users of treatments for lower urinary tract symptoms.

Specific episode of exposure to NOCDURNA will be established using information on dispensed prescriptions for NOCDURNA. Information will include drug and substance name, ATC code, formulation, strength and dispensed amount of drug, as available in each data source.

On-treatment person-time will be constructed from single prescriptions or multiple sequential prescriptions for NOCDURNA and the drugs defining the LUTS cohort. The duration of individual prescriptions for NOCDURNA will be calculated based on the days supplied, as estimated from the number of oral lyophilisates dispensed and the recommended daily dosage, one oral lyophilisate per day. The estimated end date of a prescription will be the date it was dispensed plus the days supplied. Sequentially dispensed prescriptions for NOCDURNA will be bridged into continuous on-treatment episodes if each subsequent date the drug was dispensed was within the days supplied by the preceding prescription plus a period equivalent to the days supplied multiplied by 2 (*i.e.*, the permissible gap). In case of prescription overlaps, the number of overlapping days will be added to the estimated end date of the subsequent prescription. The first treatment period will end when there is no subsequent prescription dispensed within the days supplied from the preceding prescription plus the defined permissible gap. Prescriptions of LUTS-defining drugs (ATC code G04BD or G04C) will be treated analogous to NOCDURNA in terms of permissible gap. Treatment restarts following treatment holiday will not be evaluated in this study.

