9.5.3 Sample size for primary outcome analysis

All available patients with a NOCDURNA prescription in the study time period will be included in this study. The primary objective is descriptive.

In addition to the feasibility study detailed above, NOCDURNA sales data was reviewed to estimate the available number of patients. Table 4 shows the patient estimate based on the share of NOCDURNA sales in 2018, the number of oral lyophilisates, 50% adherence, and coverage of the database per country of this study. GePaRD coverage is approximately 18% of the German population.

Table 4. Patient estimate for 2018 per country of interest	
--	--

Country	Share of NOCDURNA sales in 2018 (%)	Number of oral lyophilisates	Patient estimate assuming 50% adherence	Patient estimate from the Database
Germany	40	661.950	3.678	662
Sweden	7	117.250	651	651
Denmark	5	82.260	457	457

The patient estimate for Sweden is thus in line with the results from the feasibility study. That the coverage and availability of data from Denmark is comparable to Sweden, as both data sources rely on national registers. Taking into account the switch from the DA to GePaRD database in Germany, the order of magnitude of available patients is also in line with feasibility results from Germany.

Extrapolating the patient estimated from Table 4 to a time period 2018-2021 (end of the study time period), and assuming conservatively that sales remain constant during the time period, the number of NOCDURNA patients in this study will likely be at least:

- Germany (GePaRD): 2650
- Sweden: 2610
- Denmark: 1830

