9 EXPOSURE AND TREATMENT COMPLIANCE

9.1.1 Extent of Exposure

Exposure person-time will be defined for Nocdurna ® patients from the date of first Nocdurna ® prescription. For comparative analyses, equivalent person-time in the LUTS contextual cohort group will be defined from the index date.

Person-time observed from index date to the date of outcome or censoring event will be determined for both the Nocdurna ® group and the LUTS group.

Estimation of exposure periods: Duration of exposure to the respective study drug (Nocdurna \mathbb{R} or LUTS treatment) will be defined based on the estimated supply of drug dispensations. To estimate the supply, the total drug amount of a dispensation is converted into defined daily doses (DDDs; sex-specific DDD for Nocdurna: 25 µg for females, 50 µg for males). The days supplied added to the dispensation date will approximate the end date of a dispensation.

Overlapping dispensations: If a new dispensation of the respective study drug occurs prior to the end date of the previous dispensation, the estimated end date of the latest dispensation will be postponed by the days of overlap.

Permissible gap: If there is a gap after the estimated end date of a dispensation (i.e. there is no new dispensation of the respective study drug covering the first day after the end date of the latest dispensation), the exposure period will be extended. A period equal to the days supplied by the latest dispensation (DDD*1) will be added to the end date of the latest dispensation. In other words, the exposure period continues if a subsequent dispensation occurs within the timeframe of the permissible gap.

End of exposure period: If no subsequent dispensation occurs within the timeframe of a permissible gap, the end of the exposure period will be the last day of the permissible gap.

The above-mentioned considerations apply to both Nocdurna ® and drugs for the treatment of LUTS. For both the Nocdurna ® and LUTS groups, exposure periods start at cohort entry.

There are multiple preparations (multiple ATC codes) defining the treatment of LUTS. All those preparations are considered when defining exposure to LUTS treatment, i.e. concomitant use and switching between different preparations to treat LUTS are allowed within a patient's exposure period. In the Nocdurna ® group, however, only Nocdurna ® dispensations are considered to define exposure periods.

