Desmopressin One oral lyophilisate per day Statistical Analysis Plan	Trial Code: 000248	18 August 2021 E-Statistical Analysis Plan-25098 (1.0) Page 25 of 91
90-day supply 2nd nocdurna* dispensation 90-day supply 30-day supply 30-day overlap	90-day permissible gap 3rd nocdurna* disp 90-day sup	
	γ Continuous Nocdurna* Exposure	

*Exposure to drugs for the treatment of LUTS will be estimated analogously.

If a person in the Nocdurna group is prescribed desmopressin in a higher dose than in the Nocdurna defining dose (25 or 50 micrograms) the person-time must be stopped when this higher dose is prescribed. Observe that these drug will have the same ATC code as Nocdurna (H01BA02), but another brand name and a higher dose. In Germany the brand will be used to identify Nocdurna.

Treatment restarts following treatment holiday (larger than the permissible gap) will not be evaluated in this study

Observe that if a patient is using the last of the prescribed/dispensed drugs, the end of treatment will be the last day according to the standard dose as defined in section 5.1.4.

On treatment person-time (exposure time) will be tabulated as shown in Table 10 and graphs will be made as shown in Figure 11, Figure 12, Figure 13, and Figure 14.

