10.1.3 Sensitivity Analyses

Sensitivity analyses will be performed to assess the robustness of the study findings:

The assumptions underlying the construction of Nocdurna ® treatment episodes will be tested. The length of the permissible gap will be shortened. For overlaps of two subsequent prescriptions, beginning of the second prescription will be shifted to the end of the first reducing the permissible gap to zero days. Table shells for this sensitivity analysis are shown from Table 45 to Table 51. The estimation of prescription duration will also be examined. Instead of estimating prescription duration based on the recommended daily dose of Nocdurna ® (1 oral lyophilisate), the dose actually prescribed to the individual patient will be considered (Sweden, Denmark). This analysis will be subject to availability of data on individual dosage instructions in the database/registry. The

method for this analysis will be the following. All dosing texts will be listed in a frequency table sorted with the most frequent text at the top. This table will be moved to EXCEL and a manual coding of the 98% of the most frequent dosing text will be done. The information will be moved back into SAS and the numeric value of the dosing instruction will be used in the sensitivity analysis as described above. Only the Nocdurna ® patients will have their dosing changed in this way. If the dosing text is informing the patient to use the drug 'as needed/vid behov/as explained or similar' this will be interpreted as 0.5 tablets per day. Often will the dosing text be like this without a specific instruction to the user. Table shells for this sensitivity analysis are shown from Table 52 to Table 58. This analysis is only possible in Sweden where the prescribing text is available.

The first sensitivity with shortened gap is expected to give a lower number of events, and at the same time also reduce the exposure time so the effect on the incidence rate cannot be predicted.

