Table 41. Secondary objective 9. Incidence of all-cause mortality for patients with and without contraindications for Nocdurna ® use. Only Nocdurna ® patients

Repeat Table 38 with all-cause mortality as outcome for patients with and without contraindications for Nocdurna ® use. Only Nocdurna ® patients.

Table 42. Secondary objective 9. Incidence of major cardiovascular events for patients with and without contraindications for Nocdurna ® use. Only Nocdurna ® patients.

Repeat Table 38 with major cardiovascular events as outcome for patients with and without contraindications for Nocdurna ® use. Only Nocdurna ® patients.

Table 43. Secondary objective 9. Incidence of major venous thromboembolic events for patients with and without contraindications for Nocdurna ® use. Only Nocdurna ® patients.

Repeat Table 38 with major venous thromboembolic events as outcome for patients with and without contraindications for Nocdurna ® use. Only Nocdurna ® patients.

Table 44. Secondary objective 9. Incidence of acute exacerbation of congestive heart failure for patients with and without contraindications for Nocdurna ® use. Only Nocdurna ® patients.

Repeat Table 38 with acute exacerbation of congestive heart failure events as outcome for patients with and without contraindications for Nocdurna ® use. Only Nocdurna ® patients.

Sensitivity analysis, demographics are not repeated

Table 45. Sensitivity analysis. Incidence of symptomatic hyponatraemia in *country* with second prescription shifted to the end of the first.

Repeat Table 9 with incidence of symptomatic hyponatraemia in *country* with second prescription shifted to the end of the first as outcome.

Table 46. Sensitivity analysis. Incidence of hyponatraemia requiring hospital intensive care in *Sweden* with second prescription shifted to the end of the first.

Repeat Table 9 with Incidence of hyponatraemia requiring hospital intensive care in *Sweden* with second prescription shifted to the end of the first as outcome.

Table 47. Sensitivity analysis. Incidence of clinically significant hyponatraemia in *Denmark* with second prescription shifted to the end of the first.

Repeat Table 9 with incidence of clinically significant hyponatraemia in *country* with second prescription shifted to the end of the first as outcome.

Table 48. Sensitivity analysis. All-cause mortality in *country* with second prescription shifted to the end of the first.

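### The overlap sensitivity step repeats the main rule, and the SAP varies the permissible gap only down to zero, so late refills go untested in Germany

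*Protocol*

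**What the plan says.** - **Main overlap rule.** Protocol 9.3.1: "In case of prescription overlaps, the number of overlapping days will be added to the estimated end date of the subsequent prescription". SAP 9.1.1 says the same: "the estimated end date of the latest dispensation will be postponed by the days of overlap".
- **Main permissible gap.** Protocol 9.3.1 sets it at two times the days supplied. SAP 9.1.1 sets it at one times the days supplied by the latest dispensation.
- **Restarts.** SAP 9.1.1: "Treatment restarts following treatment holiday (larger than the permissible gap) will not be evaluated in this study". Protocol 9.3.1 agrees.
- **Sensitivity analysis in protocol 9.7.3.** The gap is to be made shorter or longer, with no lengths fixed. The overlap step reads: "For overlaps of two subsequent prescriptions, beginning of the second prescription will be shifted to the end of the first". Prescribed dose is to replace one lyophilisate per day in Sweden and Denmark, if the data exist.
- **Sensitivity analysis in SAP 10.1.3.** "The length of the permissible gap will be shortened". The overlap shift and the reduction to zero days stand in one sentence. The prescribed-dose analysis codes as-needed instructions as 0.5 tablets per day. The text limits it to Sweden, some shells among Tables 52-58 also name Denmark, and SAP Table 6 marks it not applicable for Germany.
- **Table shells.** The titles of Tables 45-51 all end "with second prescription shifted to the end of the first", while SAP Table 6 files the same tables under a reduced gap.
- **Disclosure.** SAP 13 records that lengthening was dropped. It does not record the change of the main gap from x2 to x1.

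**The concern.** A sensitivity analysis is informative only if it can give a different answer. The overlap step appears to be the main rule in other words. If so, a reader of Tables 45-51 would credit the study with a check that cannot fail.

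The second issue is direction. An episode can be closed too late (the patient has stopped, but the gap keeps the clock running) or too early (the patient refills late and is still taking the drug). Restarts are not evaluated, so an episode closed too early is never reopened, and later on-treatment time and events are lost. Protocol 9.9.2 promises to examine the robustness of both the on-treatment and the off-treatment definitions. The SAP's only gap variation moves stop dates earlier. In a study of long-term safety, the other direction also needs a check.

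**Working it through.** **1. The plan's own intake figure.** Table 4 in protocol 9.5.3 rests on "the number of oral lyophilisates, 50% adherence, and coverage of the database". Patients = lyophilisates / (360 x 0.5):
- Germany: 661,950 / 180 = 3,677.5 (stated 3,678); x 0.18 = 661.9 in GePaRD (stated 662)
- Sweden: 117,250 / 180 = 651.4 (stated 651)
- Denmark: 82,260 / 180 = 457.0 (stated 457)
- Four years: 2,648, 2,606 and 1,828 (stated 2650, 2610, 1830)

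The table reproduces. It fixes only an average of 180 lyophilisates per patient-year.

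**2. Overlap rules.** Let the first prescription end on day E, and let the second be dispensed on day d < E with supply s.
- Main rule: d + s + (E - d) = E + s.
- Sensitivity rule: start at E, end at E + s.

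These are identical for any d, E and s. With 30-day packs on days 0 and 20, the main rule gives 20 + 30 + 10 = 60 and the shift gives 30 + 30 = 60. With the SAP's illustration (90-day supplies, 30 days of overlap), both give day 180. In 50,000 simulated dispensing histories, none had a different end date. The real alternative, no carry-over, gives 20 + 30 = 50 in the first example.

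**3. What each gap bridges.** With supply s and gap g x s, a refill is bridged if it comes within s(1 + g). Steady adherence is s divided by the refill interval, so the lowest adherence bridged is 1/(1 + g). For a 90-day supply:

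| Gap | Refill accepted to | Lowest adherence bridged |
|---|---|---|
| zero (SAP sensitivity) | day 90 | 100% |
| x1 (SAP main) | day 180 | 50% |
| x2 (protocol main) | day 270 | 33% |

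This assumes no stock carried over from earlier overlaps.

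**4. What the prescribed-dose analysis adds.** At 0.5 tablets per day, 90 lyophilisates become 180 days supplied. With the x1 gap the episode runs to 180 + 180 = day 360, against 90 + 90 = day 180 in the main analysis. This does move the stop date later, but only where dosing text exists. Protocol 9.4.1.2 describes that text in Denmark as optional free text. Of the 2650 + 2610 + 1830 = 7090 expected NOCDURNA patients, Germany holds 2650 / 7090 = 37%. If only Sweden can run the analysis, (2650 + 1830) / 7090 = 63% have no later-stop check.

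**5. Illustrations only.** The distributions here are assumptions and are not in the documents.
- Refill intervals lognormal, centred on 180 days for a 90-day supply, coefficient of variation 0.10 to 0.50. Share of refills bridged: zero gap 0-11%, x1 50-59%, x2 80-100%.
- Adherence symmetric around 50%. Half of refilling patients fall below the x1 threshold. Below the x2 threshold are 33% (uniform), 14% (Beta(5,5)) or 6% (Beta(10,10)).

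**6. Which rates the gap touches.** Protocol 9.2.3.1 follows patients whether or not they are on drug and brings in end of treatment only where appropriate. Protocol 9.7.2.1 and SAP 10.1.2 run person-time to the first censoring event. On that reading the gap does not enter the primary rate. SAP 10.1.3, however, expects a shorter gap to lower both the event count and the exposure time. Both cannot describe the same rate.

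**The case against.** The strongest reply is that the section does test stop dates. The zero gap moves a single 90-day fill from day 180 to day 90. That addresses overestimated exposure, which is the error protocol 9.9.2 names. The prescribed-dose analysis moves stop dates the other way and models intermittent use directly. Protocol 9.7.3 itself permits lengthening, so the one-sided gap is an SAP choice, and SAP 13 discloses it. The redundant overlap sentence does no numerical harm, and SAP Table 6 shows what Tables 45-51 really contain.

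Most of this stands, and it rules out three stronger readings that a reader might infer:
- *That the analysis cannot test the stop-date assumption at all.* It can: earlier everywhere, and later where dosing text exists.
- *That the sponsor's 50% adherence figure demands a longer gap.* The figure converts sales into patients. An average of 180 lyophilisates a year fits packs lasting twice as long, but equally half a year of full daily use. The protocol's x2 gap already bridges 50%. Under the SAP's x1 gap a refill on the boundary day is still bridged.
- *That a zero gap cuts most patients to their first pack.* The documents give no refill distribution, and stock carried over from early refills works against this.

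The reply does not rescue the overlap step, which remains a null test named in seven table titles. Nor does it give Germany any check on episodes closed too early. SAP 13 gives no clear reason for dropping the longer gap: the reason it states follows, and appears to belong to, the added rule on same-day dispensing.

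**Conclusion.** The point holds in a limited form. The overlap step cannot change any episode end date; that is algebra and needs no assumption. The SAP varies the gap in one direction only, to zero. Misclassification from late refills is therefore examined only through the prescribed-dose analysis in Sweden and possibly Denmark. About 37% of the expected cohort (Germany) has no such check, or 63% if Denmark lacks usable text. These shares rest on the sponsor's own patient estimates.

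The bridging thresholds (100%, 50%, 33%) assume steady refills without stockpiling. How many patients are affected cannot be derived from the documents. Whether the primary rate is affected at all depends on which person-time definition applies, and the two documents leave that open. The move from x2 to x1 in the main gap is a separate change that SAP 13 should list.

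**What to change.** 1. In protocol 9.7.3 and SAP 10.1.3, replace the overlap shift with its true alternative, no carry-over: end date = last dispensing date + days supplied.
2. Restore a lengthened gap as a sensitivity analysis in all three countries, at x2 days supplied if x1 is the main rule. This is the protocol's main rule, so the run also shows the effect of the unlisted change.
3. Retitle Tables 45-51 as the zero-gap analysis, and add the change from x2 to x1, with its reason, to SAP 13.
4. Reconcile protocol 9.2.3.1, protocol 9.7.2.1 and SAP 10.1.2 with SAP 10.1.3, stating which rates use on-treatment time and so depend on the gap.

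The cost is SAP wording and reruns of the existing macro on exposure data built with changed parameters. The downside is a few additional tables per country.

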9.7.4 Meta-analyses

Assuming country-specific analyses have been completed, results for the analysis of primary and secondary outcomes that can be defined in all three countries can also be combined using a meta-analysis approach in order to achieve a more precise estimate of the observed measure of incidence rate and identify any potential country-specific patterns in the data. Incidence rates of the two different groups will be combined across the three databases. Because the current analysis will pool incidence proportions of sparse data, a logistic regression model with random intercept will be used to calculate the pooled the mean log odds, which will be back transformed to the probability scale to yield the median incidence proportion and 95% CI. A likelihood ratio test will be used to evaluate between-database heterogeneity. Database-specific incidence rates will be meta-analysed with a Poisson regression model with random intercept (25). The logarithm of the sum of patient-time at risk will be used as an offset variable to yield incidence rates per 1000 patient-years. Pooled incidence rates will be back-transformed from the logarithm scale to per 1000-patient-years unit.

9.8 QUALITY CONTROL

9.8.1 Data collection, validation and data quality control at level of sponsor representative

Data collected from claims databases and administrative (national) healthcare registries and databases in Denmark, Germany and Sweden will be used to retrieve data on the selected patient population. These are all data sources that are being used widely for research.

GePaRD is based on deterministically linked claims data. The linkage of out-patient, hospital and dispensation data is performed at each SHI provider (based on insurance member identifiers. The SHIs deliver the data to a third-party trust centre where the data is pseudonymised and delivered to BIPS according to the data protection concept. Comprehensive plausibility checks are performed before pseudonymisation, as well as before inclusion of new data into GePaRD.

In Sweden and Denmark, national registers are governed by the respective national boards of health and the national statistics agencies. In both countries, reporting of information to the health data registers is compulsory for all healthcare providers. Rigorous validation work is constantly ongoing from the health authorities to ensure that data are complete, comprehensive and with the highest quality possible. The data sources used in this project have been used extensively for research. Data quality will be further checked and assessed in the data management process. Moreover, the investigator will stay in close dialogue with the register holders to assure accuracy in the data retrieved.

